- Aim 1: To determine the efficacy of FIOC in positively affecting first-year coparenting of unmarried African American parents, relative to early coparenting of comparison families
Hypothesis 1: Families who participate in FIOC will demonstrate more cooperation and better communication in their post-natal coparenting systems at 3 and 12 months post-partum than families receiving TAU
- Aim 2: To determine the efficacy of FIOC in affecting first-year parental adjustment.
Hypothesis 2: Mothers and father who participate in FIOC will show greater decreases in depressive symptomology from prenatal to postnatal assessments than parents receiving TAU.
Hypothesis 3: Mothers and father who participate in FIOC will show lower levels of parenting stress at 3 and 12 months than families receiving TAU.
- Aim 3: To determine the efficacy of FIOC in affecting early child outcomes.
Hypothesis 4: Infants whose coparents participate in FIOC will show a more advanced

triangular capacity at 3 and 12 months

Hypothesis 5: Infants whose coparents participate in FIOC will show better regulatory and socioemotional competence at 12 months than control group children.

- Aim 4: To determine the efficacy of FIOC in affecting father involvement
Hypothesis 6: Fathers who participate in FIOC will show greater involvement at 3 and 12 months post-partum
- Aim 5: To determine whether increased father involvement is associated with better socioemotional adjustment by the baby
Hypothesis 7: Children of more involved fathers will show greater regulatory and socioemotional competence at 12 months post-partum
- Aim 6: To explore whether the FIOC intervention has an impact on the emergence of intimate partner violence (IPV)
Hypothesis 8: IPV will be more likely to emerge during the child's first year among TAU families than among families who complete the FIOC intervention
- Aim 7: To determine whether enrollment numbers, randomization rates, retention rates, and comparative RCT outcomes differ as a function of active versus passive recruitment methods for unmarried mother-father dyads.
Hypothesis 9: Proportions of enrollment and randomization and retention rates will favor families identified via self-referral (passive recruitment), while outcomes for families completing the intervention will not differentiate the two groups.

4. Study design including information needed to answer the research questions:

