This is a prospective longitudinal study using a pre-post randomized controlled treatment design that will allow comparisons of the extent to which study participants in experimental and control groups show pre-to-post changes in family functioning.

All families are seen initially for a PRE Intake assessment (Time 1), during which mothers are screened for prior or active IPV using valid, standardized instruments, an IPV Screen and the Revised-Conflict Tactics Scale (CTS2). If mothers report a history of IPV, they may under specified circumstances still be eligible to participate depending upon results of an assessment performed by trained project staff using the Danger Assessment Scale (DAS; Campbell 2003) as a screening instrument (see inclusion and exclusion criteria). If certain indicators are present in the mother's IPV screen/CTS2 assessments at baseline, the father will not be given the IPV screen/CTS2. If the father is not be given the IPV screen/CTS2 at pre-assessment, he will not be given the IPV screen/CTS2 at either post assessment time-point. The decision about whether to enroll a family reporting IPV is made in consultation with Co-PI [name] after the session concludes. Families are notified that they will receive a phone call within 48 hours appraising them of whether or not they have been chosen to take part in the study and, if they are chosen, which group (treatment or control) they will be assigned to. All families for whom levels of IPV are NOT of substantive concern and who are not found ineligible for other valid exclusion factors are randomized to one of the 2 groups and notified of their assignment. Those for whom IPV is a concern or who are ineligible for other reasons are notified that they were not selected.

For those to be enrolled (projected to be the overwhelming majority of all screened families who complete the intake process), subjects are assigned to treatment conditions through urn

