randomization, to maximize the likelihood that treatment groups will be balanced with respect to demographic variables (presence of children from prior unions) and prognostic variables (frequency of IPV). We will use a Microsoft Access-based program previously developed for the Yale Department of Psychiatry NIDA-funded Psychotherapy Development Center and used in prior studies by Co-PI [name]. In urn randomization, an algorithm modifies ongoing randomization probabilities based on prior composition of treatment groups, and maximizes multivariate equivalence of treatment groups (Stout et al., 1994). Thus, urn randomization offers the benefits of balancing allocation of important prognostic variables in treatment groups, while still retaining other benefits of random assignment (Wei, 1978).

Once enrolled, parents assigned to the treatment group are contacted by the Intake Coordinator or Resource and Referral Navigator who introduces their mentors and delivers the participants' gift cards for completing the intake assessment. Mentors arrange two initial 1-on-1 mentorship sessions with the parents, as per the FIOC protocol, after which the FIOC intervention commences. Families randomized to the control group are contacted by the Intake Coordinator or Resource and Referral Navigator, who schedules a meeting to deliver gift cards for completing the intake assessment. The R&R Navigator also provides a listing of existing Pinellas County Services and offers parents the opportunity to contact her at any time for assistance with referrals to Pinellas County services for pregnant or parenting families. All families, regardless of assignment, are also reminded about the follow-up assessments that will be completed at 3 months post-partum; and at 12 months post-partum. A formal check-in will be completed at 1-month post-partum (Congratulations on the birth card sent), and episodic newsletters and reminder texts (for families consented after January 30, 2017) will be sent at staged intervals to help keep in touch. Texts or phone calls to keep in touch will be sent to female participants by female staff only to ensure comfort of research participants.

All study participants will be offered the opportunity to be seen for initial assessments, follow-ups and mentoring sessions in person or via the Microsoft Teams platform.

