## **Cover Letter**

### **Statistical Analysis Plan**

**Document Date 1.31.2022**

**NCT03097991**

### **FIOC Statistical Analysis Plan**

- Initial descriptive summations and simple statistical tests will compare groups.

- Primary Aims 1-4: Effects of the intervention. To examine if coparenting and individual adjustment outcomes are superior for FIOC families than for control group families at 3- and 12-months post-partum two-sided independent sample t-test for equivalence will first be employed for single time point comparisons. We will test hypotheses further using linear or generalized linear models to control for potential confounding and account for imbalance between the two treatment conditions.
- For longitudinal outcomes that are continuous (measured at Baseline; 3; and 12 months post-partum) we will use repeated measures analysis of covariance (ANCOVA; Crowder & Hand, 1990) to detect if treatment and control groups perform differently at any time points. For longitudinal outcomes that are categorical, generalized linear model (GLM, McCullagh & Nelder, 1989) will be used for the same purpose. Repeated measures ANCOVA and GLM allow us to account for correlation between repeated measures and detect possible moderating/confounding between treatment effects and subject individual differences. Multiple comparison adjustment will be addressed in analyses. We will report significance under both regular (.05) and Bonferroni-adjusted alpha.
- Exploratory Aim 1: To examine whether extent of father engagement is associated with better infant socioemotional adjustment regression analyses will examine variance in infants' 12-month ITSEA Internalizing, Externalizing, Dysregulation and Competence scores explained by 3- and 12-month father engagement.
- Exploratory Aim 2: To examine whether FIOC prevents the emergence of IPV and help to prevent future IPV in couples where it was previously reported, we will first explore simple chi-square analysis to compare FIOC and TAU conditions on the binary variable of any instance of physical violence between partners reported on the CTS2 over the 12 months of follow-up. Next,

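### The only analysis of the binary IPV endpoint is an unstratified chi-square that pools new with recurrent violence, so by itself it cannot support Hypothesis 8 on emergence

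*SAP*

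**What the plan says.** SAP, Exploratory Aim 2, sets two questions: "whether FIOC prevents the emergence of IPV and help to prevent future IPV in couples where it was previously reported". Its first step is that "we will first explore simple chi-square analysis to compare FIOC and TAU conditions on the binary variable". The SAP then defines the endpoint for this test as "any instance of physical violence between partners reported on the CTS2 over the 12 months of follow-up". Nothing restricts this comparison to couples without earlier violence, and nothing stratifies it.

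Two further models follow. The first is a linear regression of the 12-month CTS2 score on arm and baseline CTS2. The second is a hierarchical regression of IPV severity on arm, severity of previous violence and their interaction.

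Protocol section 3, Hypothesis 8, is narrower than the SAP aim: "IPV will be more likely to emerge during the child's first year among TAU families than among families who complete the FIOC intervention".

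Protocol section 4 allows prior IPV at entry: "If mothers report a history of IPV, they may under specified circumstances still be eligible to participate". The same section names what the urn is meant to balance: "demographic variables (presence of children from prior unions) and prognostic variables (frequency of IPV").

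**The concern.** Two problems follow from reading these places together.

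**Interpretation.** Follow-up violence in a couple with earlier IPV is recurrence; in a couple without it, emergence. The pooled binary endpoint counts both alike. A lower rate under FIOC could come wholly from fewer recurrences, and the chi-square would look the same as if new violence had been prevented. Hypothesis 8 is about new violence only. If the chi-square is read as its test, the trial could report that FIOC prevents the emergence of IPV with no effect on emergence at all.

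**Efficiency.** The protocol treats IPV frequency as prognostic and balances allocation on it. A test that ignores a prognostic factor balanced by design uses a variance that is too large, so it rejects too rarely and loses power.

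**Working it through.** **The plan's own figure.** Protocol section 5 gives N = 120 (60 per arm), F(1,117) = 7.74 and d = .514 at power .8. Check: d = 2√(7.74/117) = .514, and the noncentral F with λ = 120 × .514²/4 gives power .797. The figure reproduces, but it is for the coparenting outcomes. Neither document gives an IPV rate, effect or power, so all IPV rates below are assumptions. Only the 60 per arm comes from the protocol.

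**Main scenario (assumed).** Prior IPV 35%, so 21 couples per arm with it and 39 without. TAU risk 60% with prior IPV and 12% without. Two-sided .05.

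1. *Make-up of TAU events.* Overall risk = .35 × .60 + .65 × .12 = .210 + .078 = .288. Share from recurrence = .210/.288 = 73%.
2. *Size with exact balance.* Pearson's test uses p(1−p) = .288 × .712 = .2051. With prior IPV balanced, the actual variance per couple is .35 × .60 × .40 + .65 × .12 × .88 = .0840 + .0686 = .1526. The ratio is .744, so the effective critical value is 1.96/√.744 = 2.27, a size of about 2.3%. Simulation gives 2.4%, and 4.9% for a Mantel-Haenszel test stratified by prior IPV.
3. *Size with chance balance.* If prior IPV is left to chance, the simulated size of the chi-square is about 5.3%. An urn lies between these limits.
4. *Power, FIOC risks 40% and 5%.* Chi-square 31% with exact balance and 33% with chance balance; Mantel-Haenszel about 40%.
5. *Effect on recurrence only (60% to 25%, emergence 12% in both arms).* Chi-square significant in 36% of trials and Mantel-Haenszel in about 40%. A test limited to couples without prior IPV rejects in about 5.6%, close to nominal.
6. *Emergence-only test, 12% v 5%.* With 39 per arm, about 39 × .12 = 4.7 v 39 × .05 = 2.0 events expected; power about 21%.

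**Wider ranges (assumed).** Prior IPV 20-50%, TAU emergence 10-20%, TAU recurrence 40-80%, exact balance:

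| Situation | Chi-square, all couples | Mantel-Haenszel | Couples without prior IPV |
|---|---|---|---|
| No effect | 1.6-4.1% | 4.7-5.3% | about 5-6% |
| Odds ratio 0.4 in both groups | 24-48% | 32-52% | 13-35% |
| Odds ratio 0.2, recurrence only | 12-67% | 15-72% | about 5-6% |
| Odds ratio 0.2, emergence only | 4-29% | 8-49% | 21-68% |
| Odds ratio 0.4, prior IPV not predictive (25% risk in both groups) | about 47% | about 46% | 26-40% |

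In the second row the gain from stratifying is about 4 to 17 points within a scenario. In the last row it vanishes. The third and fourth rows show the interpretation problem: the pooled test often reacts to recurrence alone and reacts weakly to emergence alone.

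**The case against.** **The SAP aim is joint.** It covers emergence and recurrence, and any physical violence in all couples is a reasonable endpoint for that. A reader might infer that a significant chi-square driven by recurrence is a false positive. It is not: it would be a correct answer to half of the SAP aim. What stands is that the test cannot say which half, and Hypothesis 8 asks only about the other one.

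**The plan does not stop at the chi-square.** A reader might infer that baseline IPV is ignored altogether. The later models adjust for baseline CTS2 and test treatment by previous IPV, and the fitted treatment effect at zero previous violence bears on emergence. But it does so on a score or severity scale and through an assumed functional form. No analysis of the binary endpoint uses baseline IPV or isolates couples without it.

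**The power loss is conditional.** It needs baseline IPV to predict later IPV, for which the documents give no figure, and it needs near balance. Protocol section 1 places families after the first 150 in FIOC outside the urn, and attrition disturbs balance further. This weakens the low-size figure, but it strengthens the case for adjustment, because baseline IPV may then differ between arms.

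**Stratifying alone does not isolate emergence.** Mantel-Haenszel reacts to a recurrence-only effect slightly more often than the chi-square does. Separate reporting is what isolates emergence, and it costs power when the effect is common to both groups.

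**The aim is exploratory.** This stands, and it limits the weight of the point.

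**Conclusion.** The point holds in a limited form. The one analysis of the binary IPV endpoint pools new with recurrent violence and leaves out a baseline factor that the trial randomises on. A significant result is therefore not, by itself, evidence for Hypothesis 8. This follows from the text and needs no assumed rate.

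The efficiency loss does rest on assumptions. In the main scenario the size is about 2.4% with exact balance and about 5% with chance balance, and power is 31-33% against 40% for a stratified test. The gain is about zero if baseline IPV is not predictive.

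The documents do not support a claim that the chi-square is invalid, that it always loses power, or that most follow-up events will be recurrences. The 73% in the working depends wholly on the assumed rates.

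**What to change.** In SAP Exploratory Aim 2:

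- Keep the chi-square as a descriptive comparison.
- Add a Mantel-Haenszel or logistic analysis of the binary endpoint adjusted for baseline IPV, and for children from prior unions where numbers allow, as the test of the overall effect.
- Report the arm difference with confidence intervals separately for couples without prior IPV (emergence) and with prior IPV (recurrence). State how prior IPV is defined. The mother's baseline CTS2 is the natural source, since the protocol does not give it to every father.
- Base any claim about emergence only on the couples without prior IPV.

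The change is SAP wording, since maternal IPV is assessed before randomisation. The downside is precision: about 39 couples per arm and 21% power for 12% v 5% under the assumed rates. The emergence estimate should therefore be presented as exploratory, and a non-significant result should not be read as absence of effect.

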Child Outcome Measures at Time 3: An adapted version of the Infant Toddler Social Emotional Assessment (ITSEA; Carter & Briggs-Gowan, 2006), comprised of the full Brief Infant Toddler Social Emotional Assessment (BITSEA) and select additional scale items from the longer ITSEA instrument, was developed in consultation with the scale’s author. The instrument measures both social-emotional/ behavioral problems and delays in competency for children ages 12-36 months. It is a 71-item parent-report index constituting of six sub-scales: Problem behavior, competence, compliance, negative emotionality, aggression, and sleep.

5. Sample size justification:

We employed a computer program provided by Murphy et al. (2009; the same information is available from the tables in Cohen, 1988) to compute the significance level required for a projected sample size, incorporating attrition estimates, of $N=120$ (60 each in the treatment and control groups, respectively). Assuming the null effect hypothesis and alpha set at .05 and power of .8, an $F(1, 117)$ of 7.74 with a $d = .514$ is required for significance. Keeping the null hypothesis test, alpha .05 and lowering power to .5, an $F(1, 117) = 4.03$ with a $d = .37$ is required for significance. Drawing on effect size estimates from the feasibility study, even with low power (.5) resulting in a $d=.37$ we would be positioned to establish the effect of the FIOC treatment for 10 of the 12 FIOC variables (10 of the 12 SCID-evaluated couple problem-solving and communication variables summarized earlier had a d greater than .33).

6. Sample type or inclusion and exclusion criteria for participating in the research:

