Exclusion Criteria: Families will be excluded if they: 1) demonstrate evidence of psychotic symptoms or suicidal ideation on the Brief Symptom Inventory; 2) either partner has recently (over the past 12 months) been arrested and convicted for violence (assault) perpetrated against someone other than a current or former partner who is the co-parent of one of their children; or 3) are deemed high risk or in need of more intensive intervention. Risk determination is made by weighing the parent's report on the Danger Assessment Scale (DAS). As a rule of thumb, a DAS score of 9 or higher will result in automatic exclusion from the study. However, it is also possible that even with a score below 9, the parent may disclose one or more of the following issues during administration of the DAS, any of which would result in exclusion from the study: 1) parent reports she has required medical care because of significant injuries due to his violence, 2) parent says she fears for her life, 3) parent reports that the partner has threatened with a weapon and owns a gun or has a gun in the household; 4) parent reports that the partner has threatened to kill her; 5) parent reports that violence has escalated recently; 6) parent reports the partner's use of illicit drugs such as cocaine, methamphetamines, hallucinogens, or opiates .

7. Expected results of the research (reports, materials, discussion papers, contributions to theory):

Results will equip the research team with answers to study objectives and determine whether there would be value in studying the curriculum in a future multi-site implementation trial.

8. Study Staff

- 1. [name].**, P.I. Will provide all project oversight; serve as IRB officer; ensure research integrity and compliance; chair senior staff and other relevant team meetings; supervise fidelity-monitoring efforts; oversee proper implementation of all protocols, data collection, evaluation of videotaped infant and family data, data management and entry, analyses, report writing, and dissemination of findings.

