we will conduct a linear regression model with intervention group and baseline CTS2 scores as predictors and CTS2 12-month scores as outcome variables. Next, hierarchical regression will be used to assess the main effects of the intervention group and severity of previous violence (reported on the CTS2 at baseline) on the severity of IPV over the 12 months of follow-up, and the interaction effect of FIOC x previous IPV on IPV severity at follow-up.

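### SAP Exploratory Aim 2 tests FIOC x prior IPV by linear regression on CTS2 scores with no safeguard if their spread rises with baseline severity; the interaction test could then reject too often

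*SAP*

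**What the plan says.** SAP Exploratory Aim 2 has three steps.

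1. A chi-square test compares the arms on any physical violence during follow-up.
2. A main-effects model follows: "we will conduct a linear regression model with intervention group and baseline CTS2 scores as predictors and CTS2 12-month scores as outcome variables". It has no interaction term.
3. A hierarchical regression takes arm and "severity of previous violence (reported on the CTS2 at baseline" as main effects, then tests "the interaction effect of FIOC x previous IPV on IPV severity at follow-up". This third step is where the point lies.

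The protocol (section 4, outcome measures at Times 1, 2 and 3, item 1) describes the CTS2 as a frequency-of-acts instrument. It has four subscales, separate items for respondent and partner, past-year and lifetime reference periods, and response options for acts that never happened. Fathers complete it only where the mother's screen raises no serious concern. The SAP does not say which of these scores is the outcome or the moderator, or on what scale.

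Generalized linear models appear in the SAP for Aims 1-4, but not for the CTS2 severity models. Under the longitudinal outcomes of Aims 1-4 the SAP adds: "We will report significance under both regular (.05) and Bonferroni-adjusted alpha".

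**The concern.** Scores that count acts from zero upward usually have a spread that grows with their mean. If couples with more violence at baseline also have more at 12 months, the few high-baseline couples have the most variable outcomes. They also have the most leverage on each arm's slope. Ordinary least squares assumes one common error variance, so it averages those couples' large variance over the whole sample and understates the uncertainty of the difference in slopes.

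The trial could then report that FIOC helps or harms mainly couples with prior violence when nothing differs between arms. Such a finding bears on safety, and it could influence the multi-site trial that protocol section 7 has in view. A Bonferroni threshold lowers the cut-off but does not repair a standard error that is too small.

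**Working it through.** **The plan's own figures.** Protocol section 5 assumes 120 analysed families, 60 per arm, with "alpha set at .05 and power of .8, an $F(1, 117)$ of 7.74 with a $d = .514$ is required for significance" and, "lowering power to .5, an $F(1, 117) = 4.03$ with a $d = .37$ is required for significance". With λ = 60·d²/2 and F(1, 117):

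- d = .514: λ = 30 × .2642 = 7.93, power .797 (stated .8); 2√(7.74/117) = .514.
- d = .37: λ = 30 × .1369 = 4.11, power .520 (stated .5); 2√(4.03/117) = .371.

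These reproduce to within about .02, so 60 per arm is the sample size used below. They do not address the CTS2 models. The documents state no false-positive rate for the interaction beyond the nominal .05.

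**Why the standard error can be wrong.** Fit Y = b0 + b1·A + b2·X + b3·A·X, with A the arm and X the baseline score. Then b3 is the slope in FIOC minus the slope in TAU. Within an arm, with SS = Σ(x − x̄)²:

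- true variance of the slope: Σ(x − x̄)²σᵢ² / SS²
- variance that ordinary least squares targets: (mean σᵢ²) / SS

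Their ratio is the average of σᵢ² weighted by (x − x̄)², divided by the plain average of σᵢ². It is 1 if the variance does not depend on X, and above 1 if the variance is largest where X is far from its mean. Skew alone therefore does not cause the problem; variance that rises with baseline does.

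**Simulation inputs.** From the documents: 60 per arm, plus a run at the maximum enrolment of 170, and alpha .05. Assumed: two-sided tests, 1:1 allocation, hierarchical regression meaning blockwise ordinary least squares, and every feature of the CTS2 distribution. There were 4,000 trials per scenario with no treatment effect at all, hence no interaction on any scale. Monte Carlo error is √(.05 × .95/4000) = 0.3 points at 5% and √(.4 × .6/4000) = 0.8 points at 40%. The 20 skewed scenarios were negative binomial, shared-frailty or zero-inflated lognormal, some capped: 2 with baseline unrelated to outcome and 18 with an association. A normal control was added.

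**Rejection rate of the nominal 5% test:**

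| Test | N = 120 | N = 170 |
|---|---|---|
| Interaction, normal control | 5.0% | 5.0% |
| Interaction, raw skewed scores, baseline unrelated to outcome | 5.8-6.0% | 5.7-6.0% |
| Interaction, raw skewed scores, baseline predicts outcome | 11.9-56.2% | 11.2-60.0% |
| Interaction, log(1 + score), all 20 | 3.6-19.2% | 4.2-20.2% |
| Interaction, prior IPV yes/no, all 20 | 0-13.5% | 0-14.8% |
| Interaction, raw scores with HC3, all 20 | 1.3-7.5% | 1.5-7.0% |
| Arm, main-effects model, all 20 | 3.6-5.4% | 3.5-5.1% |

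Selected scenarios at N = 120 (negative binomial variance μ + μ²/k; x is the baseline score):

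| Baseline | 12-month score | Ordinary | HC3 |
|---|---|---|---|
| mean 3, k = .2 | mean .5 + .5x, k = 1 | 56.2% | 7.2% |
| mean 3, k = .2 | mean .5 + .5x, k = 20 (near Poisson) | 49.7% | 7.5% |
| mean 15, k = .8 | mean 5 + .5x, k = 1 | 32.2% | 5.3% |
| mean 3, k = .2 | mean 2 + .1x, k = .3 (weak link) | 21.0% | 3.6% |
| mean 15, k = .8, shared frailty, capped at 50 | same | 11.9% | 6.5% |

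As a rough normal approximation, 11.9% corresponds to a standard error too small by a factor 1.96/1.56 = 1.26, and 56.2% to 1.96/0.58 = 3.4.

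**Second design.** Baseline is zero in 60% of couples and geometric in 40%; the follow-up mean is .3 + .5 × severity; 60 per arm, 2,000 trials per setting. Uncapped scores gave 29-46%, scores capped at 6 gave 21-25%, and HC3 gave 4-7%. In one uncapped setting with 500 trials, permuting arm labels gave 6.6% and negative binomial regression on log(1 + baseline) gave 4%. Both agree with 5% given a Monte Carlo error of √(.05 × .95/500) = 1.0 point.

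**The case against.** The best reply is that the size of the problem comes from assumptions. The documents give no CTS2 mean, spread, share of zeros or baseline-to-follow-up association, and no scoring rule. A log scale or a yes/no moderator removes much or all of the inflation, and the SAP's wording excludes neither, though its references to scores and severity lean towards raw scores. This stands. A reader might infer a single false-positive rate for the plan, for example 20-44%, since 12 of the 18 associated scenarios fall about there. The documents do not support that: 5 scenarios lie above, 1 below, and the two without association sit near 6%.

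Eligibility also cuts both ways. The protocol (section 6) says "a DAS score of 9 or higher will result in automatic exclusion from the study", and lists further exclusions. These may remove some of the couples who would drive the inflation. Capping does lower the rate, but not to 5% in the capped scenarios tried.

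A reader might further infer that the main-effects regression is invalid, or that both linear models must become count models. Neither follows. The arm test in that regression keeps its level. Moderation on the additive scale is a legitimate question, so a change to rate ratios is a choice of effect scale and not a correction. Nothing in the documents sizes a gain in power from a count model, and none is claimed here.

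Lastly, this is the third step of an exploratory aim. Aims 1-4 and the chi-square test, which is closest to Hypothesis 8, are untouched. That limits the priority. It does not remove the gap, because the SAP names no safeguard for a test it commits to.

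**Conclusion.** The point holds in conditional form. If raw CTS2 scores are used and the spread of the 12-month score rises with baseline severity, the interaction test with ordinary standard errors could reject a true null far more often than 5%: about 12-56% at N = 120 in the assumed scenarios where baseline predicts outcome. Enrolling 170 does not cure it. Where baseline does not predict outcome the rate is near 6%, and with a log scale or yes/no moderator it is 0-19%. These rates depend on the assumed distributions, on two-sided testing and on reading hierarchical regression as blockwise least squares. What the documents themselves establish is narrower: a moderation test on an undefined frequency score, with no provision for unequal variance. Priority is low to moderate.

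**What to change.** In SAP Exploratory Aim 2:

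- For the interaction term, replace ordinary standard errors with HC3 robust standard errors, or use a permutation test. HC3 is simpler here. The protocol (section 1) assigns families after the first 150 directly to FIOC, and a permutation test has a clear basis only for the randomised families, ideally following the urn scheme.
- Define the CTS2 score used as outcome and as moderator: subscale, reporter, reference period, and raw, transformed or categorical scale.
- Optionally, report a negative binomial model with rate ratios as a sensitivity analysis, so readers can see whether any moderation depends on the additive scale.

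The main-effects model can stay as written. The cost is a few lines of SAP text and a software option on the same data. The downside is slightly wider intervals and less apparent power for the interaction; HC3 was also somewhat conservative in places (down to 1.3%).
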